## **6. PROTECTION OF HUMAN SUBJECTS**

### **6.1. Risks to the subjects**

#### **6.1.1. Human Subjects Involvement and Characteristics**

##### ***Patient Data Registration and Collection***

If confirmed as eligible for a particular trial, the patient will be allocated a unique trial number and the treatment regimen defined. All study data will be recorded on case report forms at University College Hospital and Mayo Clinic. All research staff who enter data onto the case report form will have signed the study signature and delegation of duties log before undertaking data entry.

A password-protected, computer-based electronic database record of the study will be kept to facilitate statistical analysis. The study will be registered with the UCL data protection officer and comply with the Data Protection Act 1988. In addition, the study will be approved by the Mayo Clinic IRB and all records held in compliance with HIPPA requirements. Trial notes and source documents may be reviewed by the sponsor as part of internal audit or inspected by the regulatory authorities.

##### ***Subject selection***

If confirmed as eligible, the patient will be consented and allocated a unique trial number and the treatment regimen defined. Ethnicity data will be collected. All study data will be recorded on case report forms. All research staff who enter data onto the CRF will have signed the study signature and delegation of duties log before undertaking data entry.

##### ***Withdrawal of Patients***

When consenting to a particular trial, patients are consenting to trial treatment, trial follow-up and data collection. If a patient is withdrawn from trial treatment, follow-up and data collection will continue as per protocol. If the patient explicitly states their wish not to contribute further data to the study, the trial center should be informed in writing (letter or e-mail). Patients may be withdrawn from treatment for the following reasons:

##### ***Patient withdraws consent***

Any change in the patient's condition which justifies the discontinuation of treatment in the clinician's opinion, e.g., progression, toxicity or intercurrent illness

##### ***Laser safety***

The laser to be used will be a Opad L 690 nm, 0.3W Diode Laser or an OEM laser of similar specifications with 1% power stability. As this laser was not designed for clinical use the following extra safety measures will be adhered to above those required for routine clinical use: 1) As the laser can emit light even when no fiber is attached, a sign will be placed onto the machine warning operators to never look into the aperture, 2) A stop watch will be used to time the duration of light delivery, 3) The power output will be calibrated using a power meter. The laser will be approved for electrical safety by the hospital engineering department. This is the same laser parameters previously used at the University College London for the initial studies.

##### ***Photosensitizer protocol***

Verteporfin (benzoporphyrin derivative monoacid ring A, BPD-MA; VisudyneTM) is licensed in the UK for treatment of age-related macular degeneration and will be purchased from Novartis Pharmaceuticals UK Ltd (Surrey, UK) as a lyophilized lipid-formulated powder and stored in the Pharmacy department at UCLH. Investigational medicinal product (IMP) dispensing will be the responsibility of the clinical trial pharmacist at UCLH and dispensing records will be maintained in pharmacy. In the United States, Visudyne is available from Bausch and Lomb (Bridgewater, New Jersey) and will be stored in the Mayo Clinic Research Pharmacy at the Saint Marys Campus of the Mayo Hospital. Labeling of drug will be carried out by pharmacy and include the term 'for investigational use only'. The lyophilized lipid-formulated powder will be mixed with distilled water to a final concentration of 2 mg/ml (previously referred to as liposomal formulation) by the chief investigator or appropriate members of his team. Investigational medical product (IMP) accountability will be the responsibility of the chief investigator. The dose, time of injection, lot

number and expiry date of the IMP will be recorded in the case report form.

***Non-study Treatments***

Patients may receive all concomitant therapy deemed to provide adequate supportive care at the investigator's discretion. All such medications or other treatments taken by the patient during the study (including those initiated prior to the start of the study) will be recorded in the patient's clinical notes and on the study case

report forms. No immunotherapy, hormonal therapy (excluding contraceptives and replacement steroids), or experimental medications will be permitted for three days post-phototherapy. Any disease progression requiring other forms of specific anti-tumor therapy will be a cause for early discontinuation in the study.

### ***Discontinuation of therapy***

A patient will discontinue a study under the following circumstances: (i) If the physician thinks it would be in the best interests of the patient, (ii) If the patient requests discontinuation, or (iii) If unacceptable toxicity is seen.

#### **6.1.2. Sources of Materials**

Data to be recorded from patient interviews and medical records will consist of historical data and laboratory values necessary for the care of the patient, that impact upon potential response to PDT therapy, including the patient's current and prior biopsy results (histological tumor type) and any laboratory values pertaining to the patient's overall health status.

Patient-specific Linkage/Subject I.D.: The patients' files will be coded by an ID number, maintained in a confidential location. Access to the data will only be possible by the Principal Investigator and by a small number of study personnel who will maintain confidentiality at all times.

#### **6.1.3. Potential Risks**

##### ***Risks and Guidelines for the Prevention of Toxicity***

The major side effect of PDT is photosensitization. All patients who receive verteporfin will be photosensitive and will remain, for three to four days after injection, in subdued lighting. Bright indoor light will be permitted after the initial four day period, but patients must observe precautions to avoid exposure of the eyes and skin to direct sunlight for at least 3 days. Patients who receive verteporfin can be safely exposed to sunlight only two days after sensitization. The level of phototoxicity will vary for different areas of the body, depending on the extent of previous exposure to light. Before exposing any area of skin to direct sunlight or bright indoor light, the patient should test it for residual phototoxicity. A small area of skin should be exposed to sunlight for 10 minutes. If no phototoxicity reaction (erythema, edema, blistering) occurs within 24 hours, the patient can gradually resume normal outdoor activities, initially continuing to exercise caution and gradually allowing increased exposure. If a phototoxicity reaction occurs with the limited skin test, the patient should continue the existing precautions for another week before re-testing. As the tissue around the eyes may be more sensitive, it is not recommended that the face be used for testing. If a patient travels to a different geographical area with greater sunshine, they should retest their skin for phototoxicity. Ultraviolet (UV) sunscreens are of no value in protecting against phototoxicity reactions because photoactivation is caused by visible light. Ocular discomfort, commonly described as sensitivity to sun, bright lights, or car headlights, has also been reported in patients. For 30 days following treatment, patients should wear dark sunglasses when outdoors, and should consult their ophthalmologist if they notice any change in vision after treatment. All patients will be given information on barrier protection (hat, gloves, long sleeves etc) and an emergency

contact number will be given for patients and GPs. Similar precautions will be taken with verteporfin for a 48 hour period.

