### c.1.e Photosensitizer protocol

After diagnosis and entry criteria are confirmed, patients will receive intravenous verteporfin 0.4 mg/kg bodyweight, 60 minutes before laser activation. The drug-light interval will be recorded to the nearest minute in the case report forms, with an acceptable treatment window being 60-90 minutes. This allows for the re-positioning of the fiber if multiple sites are to be treated. Patients will remain in subdued lighting on the ward for 24 hours after injection, followed by re-adaptation to indirect sunlight for increasing periods during the morning and late afternoon of the next day. Bright indoor light will be permitted after 24 hours and exposure to direct sunlight allowed after 48 hours.

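### Sections c.1.e and 6.1.3 set incompatible light-protection periods for verteporfin, and section 6.1.3 disagrees with itself

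*Combined protocol and SAP*

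**What the plan says.** Two sections of the combined protocol and SAP tell staff how long a patient must be protected from light after verteporfin.

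Section c.1.e (Photosensitizer protocol) reads: "Patients will remain in subdued lighting on the ward for 24 hours after injection, followed by re-adaptation to indirect sunlight for increasing periods". The re-adaptation is placed on the day after injection. The section then adds: "Bright indoor light will be permitted after 24 hours and exposure to direct sunlight allowed after 48 hours".

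Section 6.1.3 (Potential Risks, under Risks and Guidelines for the Prevention of Toxicity) opens differently: "All patients who receive verteporfin will be photosensitive and will remain, for three to four days after injection, in subdued lighting". It continues: "Bright indoor light will be permitted after the initial four day period", and in the same sentence, "but patients must observe precautions to avoid exposure of the eyes and skin to direct sunlight for at least 3 days". The next sentence is "Patients who receive verteporfin can be safely exposed to sunlight only two days after sensitization". After paragraphs on skin testing, sunglasses, barrier clothing and an emergency number, the section ends: "Similar precautions will be taken with verteporfin for a 48 hour period".

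Section 6.1.3 also advises a skin test before direct sunlight or bright indoor light: ten minutes of sun on a small area, watched for a reaction over 24 hours. Section c.1.e does not mention this test.

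**The concern.** Both sections time the same precautions for the same drug. Sections c.1.b, c.1.e and the pharmacy text in 6.1.1 name only verteporfin, so the difference cannot come from two agents or two arms. A patient who starts re-adapting to indirect sunlight the day after injection is on schedule under c.1.e but should still be in subdued lighting under the opening of 6.1.3.

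This is a safety instruction for every treated patient. Section 6.1.3 calls photosensitization the major side effect of PDT, and section 6.2.2 lists photosensitivity among the expected adverse events. Ward orders or discharge advice written from one section can conflict with advice written from the other, and the two sites could work to different schedules. There is also a compliance question. Investigators must follow the current protocol (Investigators Responsibilities), and violations at Mayo go to its IRB (Trial Center). As written, the same care can count as compliant or as a deviation, depending on the section used.

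**Working it through.** The plan gives no derived figure to reproduce. The check puts each stated period into hours after injection and subtracts.

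| Item | Section c.1.e | Section 6.1.3 | Difference |
|---|---|---|---|
| Subdued lighting lasts | 24 h | 3 to 4 days = 72 to 96 h | 72 − 24 = 48 h to 96 − 24 = 72 h |
| Bright indoor light from | 24 h | after four days = 96 h | 96 − 24 = 72 h |
| Direct sunlight, minimum-period sentence | 48 h | at least 3 days = 72 h or more | at least 72 − 48 = 24 h |
| Direct sunlight, two-day sentence | 48 h | 2 days = 48 h | 48 − 48 = 0 h |
| Closing sentence on precautions | not stated | 48 h | see below |

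**Bright indoor light, other reading.** If the four-day period means the three to four days of the preceding sentence, the gap is 48 to 72 h rather than 72 h. The conflict remains.

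**Within section 6.1.3.**
- Sunlight at 48 h comes before the section's own subdued lighting ends, by 72 − 48 = 24 h to 96 − 48 = 48 h.
- Precautions for 48 h (closing sentence) stand against 72 to 96 h of subdued lighting (opening sentence), which is again 24 to 48 h apart.
- The wait for bright indoor light (four days) is longer than the minimum wait for direct sunlight (three days, or two).

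**At discharge.** Section c.1.d anticipates discharge at day 3, and section c.1.b places day 3 at two days after PDT, so about 48 h (ignoring the 60 to 90 minutes between injection and light). Subdued lighting under c.1.e has then ended, while 72 − 48 = 24 h to 96 − 48 = 48 h remain under the opening of 6.1.3. The hour of discharge is not stated. If it is assumed to fall between 40 and 56 h, the remainder is 72 − 56 = 16 h to 96 − 40 = 56 h.

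**Does the skin test join the two schedules?** If the 24-hour reading must be complete before bright indoor light at 24 h, the sun exposure would have to take place at 24 − 24 = 0 h, when both sections require subdued lighting. This is an inference, because 6.1.3 gives no time for the test.

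**Does another section decide?**
- Section a.3 says verteporfin was chosen partly for shorter photosensitivity, but gives no duration.
- Section b.1 reports no photosensitivity in the earlier study at the same verteporfin dose, but not the light precautions used there.
- The rule in section 6.5 to take the most conservative course applies to disagreement between the monitoring committees, not to conflicting protocol text.

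**Patients affected.** 15 + 15 = 30 by section c.1.b, at each treatment; section c.1.d allows up to two further treatments.

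**The case against.** Several points can be made on the other side.

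- **Section c.1.e is partly permissive.** It allows bright indoor light and sunlight after set times without requiring them, so a longer restriction would not breach those sentences. That stands. It does not cover subdued lighting, where c.1.e describes 24 hours followed by re-adaptation the next day. In the other direction, care at the c.1.e limits departs from the opening of 6.1.3.
- **The two-day sunlight sentence may be a statement about safety, not an instruction.** A rule of at least three days could simply be stricter. This is fair, and it makes the internal conflict on sunlight weaker than the conflict on subdued and indoor light.
- **The closing 48-hour sentence does not mention sunlight.** Also true: counting it as agreement with c.1.e on sunlight would be interpretation. Its plainer conflict is with the three to four days at the start of the same section. Nor does it say that it replaces the opening sentences, and 48 hours would still not match the 24 hours in c.1.e for subdued lighting and bright indoor light.
- **The skin-test and discharge-hour arithmetic is not needed.** It rests on an inference and a labelled assumption. The conclusion does not depend on either.
- **The patient leaflet may carry a single schedule, and harm is not shown.** The leaflet is outside the text reviewed. Section 6.1.3 also provides a skin test, barrier advice and an emergency number. These points reduce the likely consequence, but they do not repair the protocol text.

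**Conclusion.** The point holds. For the trial's only photosensitizer, the two sections differ by 48 to 72 hours on subdued lighting and by 72 hours on bright indoor light (48 to 72 hours on the looser reading). On direct sunlight they agree through one sentence of 6.1.3 and differ by at least 24 hours through another. Section 6.1.3 is also inconsistent internally, most clearly between its opening three to four days and its closing 48 hours.

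The conversions take a day as 24 hours and count from injection. Nothing in the documents gives one section precedence. Grading this as something that must be fixed is a judgement: it is a direct contradiction in a safety instruction that applies to every treated patient, even though harm has not been shown. It has no bearing on the sample size or the analysis.

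**What to change.** The sponsor's clinicians must reconcile sections c.1.e and 6.1.3, including the sentences within 6.1.3 that disagree, into one light-protection schedule used at both sites. The reconciled text should:

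- give a single statement each for subdued lighting, bright indoor light, indirect sunlight and direct sunlight, all counted from the same starting point;
- say whether the elements found in only one section, such as the skin test and the re-adaptation step, apply;
- be checked against the patient information leaflet and discharge instructions at both sites.

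Which periods and precautions are right is a clinical decision for the sponsor, and none is proposed here. The cost is a text correction in two sections and a check of the patient documents.

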## **6.2. ADEQUACY OF PROTECTION AGAINST RISKS**

#### **6.2.1. Recruitment and Informed Consent**

Written informed consent will be obtained from all patients according to the UCLH guidelines 'Consent for research on human subjects' or according to Human Subjects guidelines from the Mayo Clinic Institutional review board. The Investigator is required to explain the nature and purpose of the study to the patient prior to study entry. Consent to enter a particular trial must be sought from each patient or their legal representative only after a full explanation has been given, an information leaflet offered and time allowed for consideration. Signed patient consent should be obtained. The right of the patient to refuse to participate without giving reasons must be respected. When agreed by both parties, the patient will sign a consent form and be provided with a copy. One copy will be placed in the medical notes and the consent process documented. Consent will be obtained by the chief or one of the principal investigators. After the

patient has entered the trial the clinician will remain free to offer alternative treatment to that specified in the protocol at any stage, if he/she feels it is in the patient's best interest, but the reasons for doing so should be recorded. In these cases the patients remain within the study for the purposes of follow-up and data analysis. All patients are free to withdraw at any time from the protocol treatment without giving reasons and without prejudicing further treatment.

## 6.2.2. Protection Against Risk

### ***Adverse Events (Definitions)***

An Adverse Event (AE) is defined as any untoward medical occurrence in a patient or clinical investigation subject administered a pharmaceutical product regardless of the causal relationship with this treatment. Any adverse event or concurrent illness experienced by a patient during any portion of the study will be described in detail, fully evaluated and recorded on an adverse event form in the case report form by the investigator.

An *Unexpected Adverse Event* is defined as an adverse drug event the nature or incidence of which is not consistent with applicable product information.

A *Serious Adverse Event (SAE)* is defined as any untoward medical occurrence that at any drug dose results in:

- Death
- Inpatient hospitalization or prolongation of hospitalization
- A life-threatening event
- Severe or permanent disability
- Cancer (other than cancers diagnosed prior to enrolment in studies involving patients with cancer)
- Congenital anomaly

Note that as defined above, serious events, expected or not, are not necessarily causally associated with the study treatment. Those occurring during treatment and up to one month post-treatment will be reported promptly, and if assessed as a Suspected Unexpected Serious Adverse Reaction (SUSAR) within the timeframes (as specified in the Clinical Trials Regulations 2004) will be reported promptly to the appropriate authorities including the independent Data Monitoring and Ethics Committee (DMEC, see Section 5 below). The ultimate decision for the continuation of the trial lies with the DMEC.

All adverse effects will be assessed for the following:

- Severity (according to NCI toxicity criteria)
- Causality
- Expectedness (see below)
- Seriousness (see above)

### ***Expected adverse events***

- Related to the photosensitiser
- Photosensitivity
- Infusion related pain
- Vasovagal reaction
- Hypersensitivity reaction
- Related to percutaneously delivered photodynamic therapy
- Abdominal pain
- Nausea and vomiting
- Pancreatitis
- Bleeding
- Ileus
- Related to cancer progression
- Jaundice
- Anorexia and weight loss
- Cholangitis
- Duodenal obstruction
- Growth and metastasis of tumor

### ***Pre-existing medical conditions***

Any medical conditions present at baseline, which worsen after exposure to a study treatment, must be assessed and recorded as an AE on the adverse event form of the case report form.

### ***Treatment-emergent adverse events***

A treatment-emergent adverse event (TEAE) is defined as any event not present prior to exposure to study medication or any event that worsens in duration, intensity or frequency following exposure to study medication. The adverse event form of the case report form will be completed for all TEAEs.

Part of the adverse event documentation will involve the investigator making a drug related assessment. To promote consistency between investigators, the following elements should be taken into consideration along with good clinical judgment when determining the relationship of study medication to adverse event. Existence of a temporal relationship between the event and the use of the study medication Ablation of the event when the study medication is withdrawn

Reappearance or worsening of the event when the study medication is re-administered

Previous experience with the study medication or related compounds

Influence of a pre-existing condition, concomitant disease or medication, or other environmental factors

The number of elements met and good clinical judgment should be used as a guide for determining the drug-related assessment. A binary assessment scale will be used to assess causality

### ***Laboratory abnormalities***

During the course of the study the investigator will be required to comment on any laboratory values outside the reference range. A laboratory abnormality will be regarded as an AE and recorded on the adverse event form of the case report form if according to the investigators judgment the value is significantly worse than at pre-treatment (significantly worse is defined by grade 3 or 4 by the NCI Toxicity criteria, version 3).

### ***Assessment of trial safety***

Annually the sponsor will provide the main REC and the MHRA with an annual safety report (ASR). The ASR will be prepared, using the sponsor's ASR form, by the Chief investigator or a delegated PI, reviewed by the sponsor and when necessary, be referred to an independent committee (independent to the trial) such as the safety committee. This will be done in accordance with the sponsor's SOP.

## **6.3. POTENTIAL BENEFITS OF THE PROPOSED RESEARCH TO THE SUBJECTS AND OTHERS**

The patient will be counseled that he/she will not necessarily benefit directly from participation in this study. However, the possibility exists that such participation in the study will help to develop improved knowledge about the treatment of pancreatic cancer.

## **6.4. IMPORTANCE OF THE KNOWLEDGE TO BE GAINED**

The human studies described in Aims 1 and 2 of this research project may provide knowledge and techniques that lead to a form of treatment that significantly improves the length and/or quality of life for patients with pancreatic carcinoma, who currently have a dismal prognosis.

